#### 8.4.1. Solicited adverse events

#### Local (injection site) adverse events

- Pain at injection site
- Swelling at injection site

#### **General adverse events**

- Fever (defined as axillary temperature  $\geq 37.5^{\circ}$ C)
- Drowsiness
- Loss of appetite
- Irritability/fussiness

The visiting field worker will record these adverse events according to detailed SOPs available on study site during the field worker visits.

**N.B.** Temperature will be recorded on days 1 to 6 by the field worker or Principal Investigator. Should additional temperature measurements be performed at other times of day, the highest temperature will be recorded.

#### 8.5. Evaluating adverse events and serious adverse events

#### 8.5.1. Assessment of intensity

Intensity of the following AEs will be assessed as described:

Adverse Event	Intensity grade	Parameter
Pain at injection site	0	Absent
	1	Minor reaction to touch
	2	Cries/protests on touch
	3	Cries when limb is moved/spontaneously painful
Swelling at injection site		Record greatest surface diameter in mm
Fever		Record temperature in °C
Irritability/Fussiness	0	Behavior as usual
	1	Crying more than usual/ no effect on normal activity
	2	Crying more than usual/ interferes with normal activity
	3	Crying that cannot be comforted/ prevents normal activity
Drowsiness	0	Behavior as usual
	1	Drowsiness easily tolerated
	2	Drowsiness that interferes with normal activity
	3	Drowsiness that prevents normal activity
Loss of appetite	0	Appetite as usual
	1	Eating less than usual/ no effect on normal activity
	2	Eating less than usual/ interferes with normal activity
	3	Not eating at all

## Table 25Intensity scales for solicited symptoms in infants/toddlers and
children less than 6 years of age

\*Fever is defined as axillary temperature  $\ge$  37.5°C

The maximum intensity of local injection site swelling will be scored at GSK Biologicals as follows:

:	None
:	< 5 mm
:	5 to 20 mm
:	> 20 mm
	::

The maximum intensity of fever will be scored at GSK Biologicals as follows:

0	:	< 37.5°C
1	:	$37.5 - 38.0^{\circ}C$
2	:	> 38 – 39.0°C
3	:	> 39.0°C

The investigator will make an assessment of intensity for all other AEs, i.e. unsolicited symptoms, including SAEs reported during the study. The assessment will be based on the investigator's clinical judgement. The intensity of each AE and SAE recorded in the CRF or SAE Report Form, as applicable, should be assigned to one of the following categories:

- An AE which is easily tolerated by the subject, causing minimal discomfort and not interfering with everyday activities.
- 2 = An AE which is sufficiently discomforting to interfere with normal everyday activities.
  - An AE which prevents normal, everyday activities (in a young child, such an AE would, for example, prevent attendance at school/ kindergarten/ a day-care center and would cause the parents/ guardians to seek medical advice. In adults/ adolescents, such an AE would, for example, prevent attendance at work/ school and would necessitate the administration of corrective therapy).

An AE that is assessed as Grade 3 should not be confused with an SAE (serious adverse event). Grade 3 is a category utilized for rating the intensity of an event; and both AEs and SAEs can be assessed as Grade 3. An event is defined as 'serious' when it meets one of the pre-defined outcomes as described in Section 8.2.

# 8.5.2. Assessment of causality

1

3

The investigator is obligated to assess the relationship between investigational product and the occurrence of each AE/SAE. The investigator will use clinical judgement to determine the relationship. Alternative causes, such as natural history of the underlying diseases, concomitant therapy, other risk factors and the temporal relationship of the event to the investigational product will be considered and investigated. The investigator will also consult the Investigator Brochure and/or Product Information, for marketed products, in the determination of his/her assessment.

There may be situations when a SAE has occurred and the investigator has minimal information to include in the initial report to GSK Biologicals. However, it is very important that the investigator always makes an assessment of causality for every event prior to transmission of the SAE Report Form to GSK Biologicals. The investigator may change his/her opinion of causality in light of follow-up information, amending the SAE Report Form accordingly. The causality assessment is one of the criteria used when determining regulatory reporting requirements.

In case of concomitant administration of multiple vaccines, it may not be possible to determine the causal relationship of general AEs to the individual vaccines administered. The investigator should, therefore, assess whether the AE could be causally related to vaccination rather than to the individual vaccines.

All solicited local (injection site) reactions will be considered causally related to vaccination. Causality of all other AEs should be assessed by the investigator using the following question:

Is there a reasonable possibility that the AE may have been caused by the investigational product ?

- NO : The AE is not causally related to administration of the study vaccine(s). There are other, more likely causes and administration of the study vaccine(s) is not suspected to have contributed to the AE.
- YES : There is a reasonable possibility that the vaccine(s) contributed to the AE.

Non-serious and serious AEs will be evaluated as two distinct events. If an event meets the criteria to be determined "serious" (see Section 8.2 for definition of serious adverse event), it will be examined by the investigator to the extent to be able to determine ALL contributing factors applicable to each serious adverse event.

Other possible contributors include:

- Medical history
- Other medication
- Protocol required procedure
- Other procedure not required by the protocol
- Lack of efficacy of the vaccine(s), if applicable
- Erroneous administration
- Other cause (specify).

# 8.6. Follow-up of adverse events and serious adverse events and assessment of outcome

After the initial AE/SAE report, the investigator is required to proactively follow each subject and provide further information to GSK Biologicals on the subject's condition.

All AEs and SAEs documented at a previous visit/contact and designated as not recovered/not resolved or recovering/resolving will be reviewed at subsequent visits/contacts.

Investigators will follow-up subjects:

- with SAEs or subjects withdrawn from the study as a result of an AE, until the event has resolved, subsided, stabilized, disappeared, the event is otherwise explained, or the subject is lost to follow-up;
- or, in the case of other non-serious AEs, until they complete the study or they are lost to follow-up.

Clinically significant laboratory abnormalities will be followed up until they have returned to normal, or a satisfactory explanation has been provided. Additional

information (including but not limited to laboratory results) relative to the subsequent course of such an abnormality noted for any subject must be made available to the Study Monitor.

GSK Biologicals may request that the investigator perform or arrange for the conduct of supplemental measurements and/or evaluations to elucidate as fully as possible the nature and/or causality of the AE or SAE. The investigator is obliged to assist. If a subject dies during participation in the study or during a recognized follow-up period, GSK Biologicals will be provided with a copy of any available post-mortem findings, including histopathology and verbal autopsies.

New or updated information will be recorded on the originally completed SAE Report Form, with all changes signed and dated by the investigator. The updated SAE report form should be resent to GSK Biologicals within 24 hours of receipt of the follow-up information as outlined in Section 8.7.1.

Outcome of any non-serious AE occurring within 30 days post-vaccination (i.e. unsolicited AE) or any SAE reported during the entire study will be assessed as:

- Recovered/resolved
- Not recovered/not resolved
- Recovering/resolving
- Recovered with sequelae/resolved with sequelae
- Fatal (SAEs only).

# 8.7. Prompt reporting of serious adverse events to GSK Biologicals

# 8.7.1. Time frames for submitting serious adverse event reports to GSK Biologicals

SAEs will be reported promptly to GSK and MVI at PATH once the investigator determines that the event meets the protocol definition of an SAE. The investigator or designate will fax or send electronically the SAE reports to GSK Biologicals' Study Contact for Serious Adverse Event Reporting **WITHIN 24 HOURS OF HIS/HER BECOMING AWARE OF THESE EVENTS**. Additional or follow-up information relating to the initial SAE report is also to be reported to the GSK Biologicals' Study Contact for Serious Adverse Event Reporting and the MVI at PATH contact within 24 hours of receipt of such information.

# 8.7.2. Completion and transmission of serious adverse event reports to GSK Biologicals

Once an investigator becomes aware that a SAE has occurred in a study subject, she/he will report the information to GSK and MVI at PATH within 24 hours as outlined in Section 8.7.1. The SAE Report Form will always be completed as thoroughly as possible

with all available details of the event, signed by the investigator (or designee), and forwarded to GSK and MVI at PATH within the designated time frames. If the investigator does not have all information regarding an SAE, he/she will not wait to receive additional information before notifying GSK and MVI at PATH of the event and completing the form. The form will be updated when additional information is received and forwarded to GSK and MVI at PATH **WITHIN 24 HOURS** as outlined in Section 8.7.1.

The investigator will always provide an assessment of causality at the time of the initial report as described in Section 8.5.2.

Facsimile (Fax) or electronic transmission of the SAE Report Form are the preferred methods to transmit this information to the Study Contact for Reporting SAEs. In rare circumstances and in the absence of facsimile equipment or electronic connection, notification by telephone is acceptable, with a copy of the SAE Report Form to follow. Initial notification via the telephone does not replace the need for the investigator to complete and sign the SAE Report Form within 24 hours as outlined in Section 8.7.1.

In the event of a death or SAE, determined by the investigator to be related to vaccination, sending of the fax or electronic report must be accompanied by telephone call to the Study Contact for Reporting SAEs.

# 8.8. Regulatory reporting requirements for serious adverse events

The investigator will promptly report all SAEs to GSK in accordance with the procedures detailed in Section 8.7. GSK Biologicals has a legal responsibility to promptly notify, as appropriate, both the local regulatory authority and other regulatory agencies about the safety of a product under clinical investigation. Prompt notification of SAEs by the investigator to the Study Contact for Reporting SAEs is essential so that legal obligations and ethical responsibilities towards the safety of other subjects are met.

The investigator, or responsible person according to local requirements, will comply with the applicable local regulatory requirements related to the reporting of SAEs to regulatory authorities and the IRB/IEC.

This protocol has been filed under an Investigational New Drug (IND) application with the US Food and Drug Administration (FDA). A given SAE may qualify as an IND Safety Report if the SAE is both attributable to the investigational product and unexpected. In this case, all investigators filed to the IND (and associated INDs for the same compound) will receive an Expedited Investigator Safety Report (EISR), identical in content to the IND Safety Report submitted to the FDA.

EISRs are prepared according to GSK Biologicals' policy and are forwarded to investigators as necessary. An EISR is required for:

- development compounds (i.e. compounds not marketed), if the event is serious, unexpected and has a suspected relationship to study drug treatment. Expected adverse events for development compounds will be described in the Development Core Safety Information (DCSI) in the Investigator Brochure (IB).
- marketed compounds (i.e. approved in at least one market), if the event is serious, unexpected and has a suspected relationship to treatment with a GSK product AND is a significant new emerging safety issue. Expected adverse events for marketed compounds will be described in the Core Safety Information (CSI). An EISR is required if an SAE was expedited to the IND in the US or to fulfill regulatory obligations in other countries. An EISR for Post marketing surveillance (PMS)/Phase IV studies would not typically be required.

The purpose of the EISR is to fulfill specific regulatory and Good Clinical Practice (GCP) requirements, regarding the product under investigation.

When a site receives an Initial or Follow-up EISR or other safety information (e.g., revised Investigator Brochure) from GSK Biologicals, the responsible person according to local requirements is required to promptly notify his or her IRB/IEC.

# 8.9. Post study adverse events and serious adverse events

A post-study AE/SAE is defined as any event that occurs outside of the AE/SAE detection period defined in Section 8.4. Investigators are not obligated to actively seek AEs or SAEs in former study participants.

However, if the investigator learns of any SAE, including a death, at any time after a subject has been discharged from the study, and he/she considers the event reasonably related to the investigational product, the investigator will promptly notify the Study Contact for Reporting SAEs.

# 8.10. Pregnancy

Not applicable

# 8.11. Treatment of adverse events

Treatment of any adverse event is at the sole discretion of the investigator and according to current good medical practice. Any medication administered for the treatment of an AE should be recorded in the subject's CRF according to Section 6.9.

# 9. SUBJECT COMPLETION AND WITHDRAWAL

# 9.1. Subject completion

A subject who returns for the concluding visit/is available for the concluding contact foreseen in the protocol is considered to have completed the study.

A subject that comes for Clinic Visit 11 has completed the double-blind phase of the study. A subject that comes for Clinic Visit 12 has completed the single-blind phase of the study.

# 9.2. Subject withdrawal

The parent(s) or guardian(s) of subjects that are withdrawn or withdraw prior to completion of a 3-dose course of TETRActHib will be advised to complete their child's routine infant immunization with the EPI services.

Subjects who are withdrawn for AEs must be clearly distinguished from subjects who are withdrawn for other reasons. Investigators will follow subjects who are withdrawn as result of a SAE/AE until resolution of the event (see Section 8.6). Withdrawals will not be replaced.

# 9.2.1. Subject withdrawal from the study

From an analysis perspective, a 'withdrawal' from the study is any subject who was not available for the concluding contact foreseen in the protocol. A subject that comes for Clinic Visit 11 has completed the double-blind phase of the study. A subject that comes for Clinic Visit 12 has completed the single-blind phase of the study.

A subject qualifies as a 'withdrawal' from the study when no study procedure has occurred, no follow-up has been performed and no further information has been collected for this subject from the date of withdrawal/last contact.

Investigators will make an attempt to contact those subjects who do not return for scheduled visits or follow-up.

Information relative to the withdrawal will be documented on the Study Conclusion page of the CRF. The investigator will document whether the decision to withdraw from the study was made by the subject's parent or guardian or the investigator and which of the following possible reasons was responsible for withdrawal:

- serious adverse event
- non-serious adverse event
- protocol violation (specify)
- consent withdrawal, not due to an adverse event
- moved from the study area
- lost to follow-up
- other (specify).

#### 9.2.2. Subject withdrawal from investigational product

A 'withdrawal' from the investigational product is any subject who does not receive the complete treatment, i.e. when no further planned dose is administered from the date of withdrawal. A subject withdrawn from the investigational product may not necessarily be withdrawn from the study as further study procedures or follow-up may be performed (safety or immunogenicity) if planned in the study protocol.

Information relative to premature discontinuation of the investigational product will be documented on the Vaccine Administration page of the CRF. The investigator will document whether the decision to discontinue further vaccination/treatment was made by the subject's parent or guardian or the investigator and which of the following possible reasons was responsible for withdrawal:

- serious adverse event;
- non-serious adverse event;
- other (specify).

# 10. DATA EVALUATION: CRITERIA FOR EVALUATION OF OBJECTIVES

#### 10.1. Primary Endpoints

#### 10.1.1. Primary endpoint; safety

• Occurrence of SAEs from the time of first TETRActHib vaccination until months 6 post Dose 1

#### **10.2.** Secondary endpoints

#### 10.2.1. Secondary endpoints for Safety

• Occurrence of unsolicited AEs after Dose 1, 2 and 3 of TETRActHib over a 14 day follow-up period (day of vaccination and 13 subsequent days)

- Occurrence of unsolicited AEs after Dose 1 and 2 of RTS,S/AS02D or Engerix-B over a 14 day follow-up period (day of vaccination and 13 subsequent days)
- Occurrence of unsolicited AEs after Dose 3 of RTS,S/AS02D or Engerix-B over a 30 day follow-up period (day of vaccination and 29 subsequent days)
- Occurrence of solicited general and local reactions over a 7 day follow-up period (day of vaccination and 6 subsequent days) after TETRActHib
- Occurrence of solicited general and local reactions over a 7 day follow-up period (day of vaccination and 6 subsequent days) after RTS,S/AS02D or Engerix-B.

# **10.2.2.** Secondary endpoints for Immunogenicity

Endpoints assessed one month post Dose 3 of RTS, S/AS02D or Engerix-B; assessment of non-inferiority:

• Anti-HBs antibody titers; difference between groups in percent seroprotection <10%

Endpoints assessed prior to vaccination, 1 month post Dose 3 of RTS,S/AS02D or Engerix-B:

• Anti HBs antibody titers

Endpoints assessed prior to vaccination, 1 month post Dose 3, 3/2 months post Dose 3 of RTS,S/AS02D or Engerix-B:

• Anti-CS antibody titers.

Endpoints assessed 1 month post Dose 3 of TETRActHib:

- Anti-diphtheria antibody titers measured by ELISA
- Anti-tetanus antibody titers measured by ELISA
- Anti-BPT antibody titers measured by ELISA
- Anti-PRP antibody titers measured by ELISA

# **10.2.3.** Secondary endpoints for Proof of concept

- The time to first malaria infection (first recording of infection of asexual stage falciparum parasites detected by the active detection of infection surveillance) over a period starting 14 days after last vaccination with RTS,S/AS02D extending for 12 weeks.
- The asexual *P. falciparum* parasitemia (prevalence and density) at 3/2 months post Dose 3 (Month 6).

# **10.3.** Tertiary Endpoints

#### 10.3.1. Tertiary endpoints for Safety

• Occurrence of serious adverse events during the single-blind surveillance period (from Month 7 to Month 14 inclusive).

#### **10.3.2.** Tertiary endpoints for Immunogenicity

Endpoints assessed 12 months post Dose 3:

- Anti HBsAg antibody titers
- Anti-CS antibody titers.

# 10.4. Exploratory Endpoints

From Day 0 and extending to 3/2 months post Dose 3 of Engerix-B or RTS, S/AS02D

• The time to the first clinical episode of symptomatic *P. falciparum* malaria (defined as the presence of *P. falciparum* asexual parasitemia above 500 per  $\mu$ L on Giemsa stained thick blood films AND the presence of fever [axillary temperature  $\geq$  37.5°C] at the time of presentation) detected by passive case detection.

From Day 0 and extending to 3/2 months post Dose 3 of Engerix-B or RTS, S/AS02D

• The time to the first clinical episode of symptomatic *P. falciparum* malaria (defined as the presence of *P. falciparum* asexual parasitemia above 500 per µL on Giemsa stained thick blood films AND the presence of fever [axillary temperature ≥ 37.5°C] at the time of presentation) detected by passive case detection and active case detection.

#### From Day 0 and extending to 14 months post Dose 3 of Engerix-B or RTS, S/AS02D

- The time to the first clinical episode of symptomatic *P. falciparum* malaria (defined as the presence of *P. falciparum* asexual parasitemia above 500 per  $\mu$ L on Giemsa stained thick blood films AND the presence of fever [axillary temperature  $\geq$  37.5°C] at the time of presentation) detected by passive case detection.
- The total number of clinical episodes of symptomatic *P. falciparum* malaria (defined as the presence of *P. falciparum* asexual parasitemia above 500 per  $\mu$ L on Giemsa stained thick blood films AND the presence of fever [axillary temperature  $\geq$  37.5°C] at the time of presentation) detected by passive case detection.

# Endpoint assessed at screening, 1 month post Dose 3 and 3/2 months post Dose 3 of Engerix-B or RTS,S/AS02D

• The frequency of CS-specific CD4+ and CD8+ T cells, as measured by intracellular cytokine staining.

# 10.5. Estimated sample size

In the study area there are approximately 30 births per month. We have assumed that 25% of children will not meet eligibility criteria; given the previous experience at the site and the estimated rates of Hepatitis B chronic carriage and HIV prevalence in antenatal women. A loss to follow up rate of 10% is anticipated and therefore 220 subjects will be enrolled to provide 200 evaluable subjects at study conclusion.

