	• This sample size will have 90% power at a 2.5% significance level using a one-sided equivalence test of proportions when the proportion that are seroprotected in the control group (subjects vaccinated with Engerix-B) is at least 0.97 and the proportion in the RTS,S/AS02D group is 0.97 and the maximum allowable difference between these proportions that still results in equivalence (the range of equivalence) is 0.10 (PASS 2000, one sided equivalence test of proportions, alpha = 2.5%).
	• Assuming an attack rate of 75% in the Control Group over the 3- month surveillance period, 100 evaluable subjects per group are needed in order to have 90% power to show a Vaccine Efficacy (=1-hazard ratio) of 45%. This is equivalent to an attack rate in the Vaccinated Group of 53.3%. Using proportion of subjects with malaria infection over the surveillance period, a Vaccine Efficacy (=1-risk ratio) of 29% can be detected with 90% power.
Number of subjects	The necessary number of infants will be screened to enroll approximately 220 infants to the study. It is anticipated that approximately 10% of enrolled infants will drop out of the study, resulting in approximately 200 subjects evaluable.
Primary	Safety
endpoint	• Occurrence of SAEs from the time of first TETRActHib vaccination until month 6 post Dose 1
Secondary	Safety
endpoints	• Occurrence of unsolicited AEs after Dose 1, 2 and 3 of TETRActHib over a 14 day follow-up period (day of vaccination and 13 subsequent days)
	• Occurrence of unsolicited AEs after Dose 1 and 2 of RTS,S/AS02D or Engerix-B over a 14 day follow-up period (day of vaccination and 13 subsequent days)
	• Occurrence of unsolicited AEs after Dose 3 of RTS,S/AS02D or Engerix-B over a 30 day follow-up period (day of vaccination and 29 subsequent days)
	• Occurrence of solicited general and local reactions over a 7 day follow-up period (day of vaccination and 6 subsequent days) after TETRActHib
	• Occurrence of solicited general and local reactions over a 7 day follow-up period (day of vaccination and 6 subsequent days) after RTS,S/AS02D or Engerix-B.

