Evaluable:	Meeting all eligibility criteria, complying with the procedures defined in the protocol, and, therefore, included in the according-to-protocol (ATP) analysis (see Sections 4.3 and 4.4 for details on criteria for evaluability).
Investigational product:	A pharmaceutical form of an active ingredient or placebo being tested or used as a reference in a clinical trial, including a product with a marketing authorization when used in a way different from the approved form, or when used for an unapproved indication, or when used to gain further information about an approved use. The investigational products for this study are RTS,S/AS02D, Engerix-B and TETRActHib.
Local Safety Monitor (LSM):	The overall role of the Local Safety Monitor, an experienced physician based in-country, will be to support the study investigators and to act as a link between the investigators and the Data Safety Monitoring Board (DSMB) (see Section 5.1.4 for further details).
Medical Monitor:	An individual medically qualified to assume the responsibilities of the sponsor (GSK Biologicals) especially in regards to the ethics, clinical safety of a study and the assessment of adverse events.
Protocol amendment:	ICH defines a protocol amendment as: "A written description of a change(s) to or formal clarification of a protocol." GSK Biologicals further details this to include a change to an approved protocol that affects the safety of subjects, scope of the investigation, study design, or scientific integrity of the study.
Protocol administrative	A protocol administrative change addresses changes to only logistical or administrative aspects of the study.
change:	N.B. Any change that falls under the definition of a protocol amendment (e.g. a change that affects the safety of subjects, scope of the investigation, study design, or scientific integrity of the study) MUST be prepared as an amendment to the protocol.
Randomization:	Process of random attribution of treatment to subjects in order to reduce bias of selection
Solicited adverse event:	Adverse events (AEs) to be recorded as endpoints in the clinical study. The presence/occurrence/intensity of these events is actively solicited from the subject or an observer during a specified post-vaccination follow-up period.

Study Monitor:	An individual assigned by the sponsor who is responsible for assuring proper conduct of a clinical study.

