#### 1.3.3.4. Phase II pediatric trial of RTS,S/AS02D; Bridging Study (Malaria-034)

Malaria-034 was a phase I/II randomized double-blind bridging study to evaluate the safety and immunogenicity of 3 doses of GlaxoSmithKline Biologicals' candidate vaccine RTS,S/AS02D (0.5 mL dose) in comparison to 3 doses of the existing formulation RTS,S/AS02A (0.25 mL dose) administered to children aged 3 to 5 years living in a malaria-endemic region of Mozambique. Both vaccines contain the same constituents but the final volume was adjusted to be compatible with existing EPI practices.

Two hundred children were enrolled into two groups of 100 subjects each, of which 189 (93 of whom received RTS,S/AS02D [D group] and 96 received RTS,S/AS02A [A group]) subjects were included in the ATP analysis of safety and reactogenicity and 143 (67 and 76 subjects respectively) subjects in the analysis of immunogenicity.

The safety profile of the two vaccine formulations was similar. Solicited symptoms were as shown in Table 14, with pain the more frequent local symptom and fever the most frequent general symptom reported. Symptoms were generally mild to moderate in intensity, and decreased in frequency with subsequent doses.

Unsolicited symptoms were reported following 69 (24.7%) doses in the RTS,S/AS02D group and following 56 (19.4%) in the RTS/SAS02A group. The most frequently reported symptoms were malaria (18% of the subjects in the D group and 25% in the A group) and upper respiratory tract infection (14% of the subjects in the D group and 12% in the A group). An unsolicited symptom, injection site erythema, deemed to be related to vaccination was reported for a single subject, following one dose in the D group. Three

symptoms in the D group and 8 in the A group were graded 3 in intensity, none of which were related to vaccination.

One serious adverse event occurred in a subject in the A group. This subject had severe malaria which lasted 4 days and required hospitalization. The subject recovered and the event was deemed by the investigator to be unrelated to vaccination.

Group		R	S,S/AS02D	) (N = 93)		R	TS,S/AS02	A (N = 96)	
		n	%	95	% CI	n	%	95%	6 CI
Pain	Any	31	33.3	23.9	43.9	43	44.8	34.6	55.3
	Grade 3	2	2.2	0.3	7.6	1	1.0	0.0	5.7
Swelling	Any	8	8.6	3.8	16.2	23	24.0	15.8	33.7
Ū	Grade 3	1	1.1	0.0	5.8	4	4.2	1.1	10.3
Drowsiness	Any	12	12.9	6.8	21.5	8	8.3	3.7	15.8
	Grade 3	2	2.2	0.3	7.6	1	1.0	0.0	5.7
Fever	Any	26	28.0	19.1	38.2	25	26.0	17.6	36.0

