# 10.5.2. Sample size for secondary endpoint immunology of Hepatitis B response

This study will compare the immunogenicity of RTS,S/AS02D to Engerix-B. A noninferiority approach will be used to calculate the power of the study for the comparison of seroprotection rates and geometric mean titers of anti-HBs antibodies. The assessment of the anti-HBs antibody immune response will be based on approximately 200 evaluable subjects (100 subjects per group). This sample size will have 90% power at a 2.5% significance level using a one-sided equivalence test of proportions when the proportion that are seroprotected in the control group (subjects vaccinated with Engerix-B) is at least 0.97 and the proportion in the RTS,S/AS02D group is 0.97 and the maximum allowable difference between these proportions that still results in equivalence (the range of equivalence) is 0.10 (PASS 2000, one sided equivalence test of proportions, alpha = 2.5%).

Similarly this sample size will provide 98.5% power to demonstrate at a 5% significance level using an equivalence of means test, that the lower limit of a two sided 95% confidence interval on the GMT ratio of anti-HBs antibodies (RTS,S/AS02D vaccine

group over Engerix-B vaccine group ) is greater than 0.5 (2 fold decrease). (PASS 2000, equivalence of means, alpha = 5%). The standard deviation used for this calculation was 0.52 (computed on log base 10 transformed titers) and was derived from a GSK Biologicals study (Malaria-034) on 67 subjects which received three doses of RTS,S/AS02D administered at a 0, 1, 2 months schedule.

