# 10.8.3. Analyses of immunogenicity

The primary analysis will be based on the ATP cohort for analysis of immunogenicity. If the percent of enrolled subjects excluded from this ATP cohort is more than 5%, a second analysis based on the Total Vaccinated cohort will be performed to complement the ATP analysis.

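### The 90% power for hepatitis B non-inferiority does not cover every Engerix-B rate of 0.97 or more, and the 220-to-200 step allows for loss to follow-up but not for other losses from the ATP cohort

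*Protocol*

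**What the plan says.** **Power claim.** Section 10.5.2, repeated in the synopsis, says: "This sample size will have 90% power at a 2.5% significance level using a one-sided equivalence test of proportions". The inputs are 100 evaluable infants per arm, a range of equivalence of 0.10, and a control seroprotection rate that "is at least 0.97 and the proportion in the RTS,S/AS02D group is 0.97 and the maximum allowable difference" between them. So the control rate is given as a floor and the RTS,S/AS02D rate as a single value.

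**From enrolled to evaluable.** Section 10.5 says: "A loss to follow up rate of 10% is anticipated and therefore 220 subjects will be enrolled to provide 200 evaluable subjects". The sentence goes on to place this at study conclusion. The synopsis (Number of subjects) says: "It is anticipated that approximately 10% of enrolled infants will drop out of the study, resulting in approximately 200 subjects evaluable".

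**Meaning of evaluable.** The Glossary defines an evaluable subject as one meeting all eligibility criteria, "complying with the procedures defined in the protocol, and, therefore, included in the according-to-protocol (ATP) analysis".

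**Cohort tested.** Section 10.8.3 says: "The primary analysis will be based on the ATP cohort for analysis of immunogenicity". A Total Vaccinated analysis is added if more than 5% of enrolled subjects are excluded. Section 10.8.3.1 declares non-inferiority if the lower limit of the two-sided 95% CI for the difference (RTS,S/AS02D minus Engerix-B) is above -0.10. It does not name the interval method.

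**Earlier retention.** Section 1.3.3.4 reports that the bridging study Malaria-034 enrolled 200 children and had "143 (67 and 76 subjects respectively) subjects in the analysis of immunogenicity".

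**The concern.** Two separate points bear on the same printed 90%.

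1. With RTS,S/AS02D fixed at 0.97, any control rate above 0.97 makes the true difference negative and uses up part of the 0.10 margin. A control rate of 0.97 is therefore the most favourable value that the wording allows, not the least favourable.

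2. Infants can leave the ATP immunogenicity cohort without being lost to follow-up. Visit intervals determine evaluability (section 5.3, Table 21). An infant who cannot be vaccinated within 7 days of schedule stays in the study but gets no further study doses (section 5.1.11). Elimination criteria apply (section 4.5), and missing titers are not replaced (section 10.7). The 10% is not described as covering any of these.

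Anti-HBs non-inferiority is the only immunogenicity objective with a formal decision rule. If it were missed, the result would be read against a 90% that holds for a narrower set of inputs than the text says.

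**Working it through.** **Inputs.** Margin d = 0.10, one-sided alpha 0.025 (z = 1.96), 1:1 allocation, 100 per arm, RTS,S/AS02D rate pT = 0.97 (sections 6.4.1 and 10.5.2). Control rate pC = 0.97 or more.

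**Formula (Farrington-Manning score test, normal approximation).**
Power = Phi{[(pT - pC + d) - z x s0] / s1}, where
- s1 = sqrt{[pT(1 - pT) + pC(1 - pC)] / n};
- s0 is the same expression at the maximum-likelihood rates restricted to a difference of exactly -0.10.

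**Step 1: reproduce the printed figure.** At pT = pC = 0.97 and n = 100 the restricted rates are 0.8836 and 0.9836.
- s0 = sqrt[(0.8836 x 0.1164 + 0.9836 x 0.0164)/100] = 0.0345
- s1 = sqrt[2 x 0.97 x 0.03/100] = 0.0241
- (0.10 - 1.96 x 0.0345)/0.0241 = 1.34, so power = 91.0%

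Exact enumeration with the score interval gives 93.3%. The printed 90% is reproduced. At 220 x 0.9 = 198, i.e. 99 per arm, the score figure is still 90.7%.

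**Step 2: raise the control rate, n = 100, RTS,S/AS02D held at 0.97.**

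| Control rate | Difference + 0.10 | s0 | s1 | Score power | Exact power |
|---|---|---|---|---|---|
| 0.97 | 0.10 | 0.0345 | 0.0241 | 91.0% | 93.3% |
| 0.98 | 0.09 | 0.0331 | 0.0221 | 87.2% | 89.6% |
| 0.99 | 0.08 | 0.0316 | 0.0197 | 81.9% | 84.9% |
| 1.00 | 0.07 | 0.0300 | 0.0171 | 74.4% | 81.8% |

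**Step 3: reduce the ATP number, 0.97 in both arms.** Malaria-034 retention is 143/200 = 71.5%, and 110 x 0.715 = 78.65, about 79 per arm. The value 91 per arm (91/110 = 83%) is a milder illustration.

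| n per arm | s0 | s1 | Score power | Exact power |
|---|---|---|---|---|
| 91 | 0.0362 | 0.0253 | 87.5% | 90.6% |
| 79 | 0.0388 | 0.0271 | 81.1% | about 83% |

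By the score method, 98 per arm is the smallest number that reaches 90%. That is 98/110 = 89% of those enrolled, so a 10% loss uses nearly all the slack.

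**Step 4: the interval method.** A Wald interval gives an exact power of 96.8% at 100 per arm and 93.7% at 79. It does not reproduce the printed 90%. Malaria-026 (section 1.3.3.3.9, Table 10) used a standardized asymptotic interval, which is of the score type.

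**The case against.** **The earlier data point the other way.** RTS,S/AS02A against Engerix-B gave 100.0% against 91.9% in Malaria-026 and 96.3% against 95.2% in Malaria-025. RTS,S/AS02D gave 100% in Malaria-034. If RTS,S/AS02D were 0.98 against a control of 0.97, score power would be 91.7% even at 79 per arm. At the Malaria-026 rates it would be about 100%. This stands: actual power may well exceed 90%. It does not repair a statement that fixes RTS,S/AS02D at 0.97 and leaves the control rate open upwards.

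**The retention figure is borrowed.** Malaria-034 enrolled children aged 3 to 5 years, and the protocol does not say why 143 remained when 189 of 200 were in its ATP safety analysis. This stands, and so 81% is a scenario, not a forecast.

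**Part of the 10% falls after the test.** The allowance runs to study conclusion (Clinic Visit 12, Month 14), while non-inferiority is tested at Clinic Visit 10 (Day 104). Some of it is therefore free to absorb other ATP losses. This stands in part, but the protocol does not give the split. Exact score power also remains 90.8% at 90 per arm, so moderate losses do little harm.

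**The interval is not named.** This may be settled in the analysis plan, and a Wald interval would keep power above 90% at 79 per arm with 0.97 in both arms. That also stands.

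**A stronger reading.** A reader might infer that 90% requires exactly 0.97 in both arms. It does not: 0.98 in both arms at 100 per arm gives 96.3%. A reader might also combine the two points (79 per arm with control at 0.98 to 1.00 gives 75.3% down to 57.9%) and call the design underpowered. That needs Engerix-B to be better than RTS,S/AS02D, which none of the earlier comparisons in the protocol shows.

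**Conclusion.** The concern holds as a correction to what is stated, not as a fault in the design or an error in the calculation itself. The 90% is correct at 0.97 in both arms with 100 per arm.

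- **Control rate.** The claim is wrong for control rates above 0.97 with RTS,S/AS02D at 0.97. The shortfall by the score method is about 3 points at 0.98, 8 at 0.99 and 16 at 1.00 (90 minus 87.2, 81.9 and 74.4). This rests only on the protocol's own inputs and a score-type test.
- **ATP number.** The step to 200 evaluable allows for loss to follow-up only. At the bridging study's retention, power at 0.97/0.97 would be about 81% (exact 83%). This rests on carrying a retention rate from older children to infants.

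The two ranges answer different questions and should not be merged into one. It is also tempting to carry the 71.5% into the log-rank power of section 10.5.3. The documents do not support that: the ATP efficacy cohort (section 10.6.4) is defined separately from the immunogenicity cohort, and an immunogenicity retention rate says nothing direct about it.

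**What to change.** Keep enrolment at 220, and leave the test, margin and decision rule as they are.

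- **Section 10.5.2 and synopsis:** replace *at least 0.97* for Engerix-B with *0.97*, or tabulate power at 100 per arm for control rates 0.97, 0.98 and 0.99 with RTS,S/AS02D at 0.97 (91.0%, 87.2%, 81.9% by the score method). Name the method used.
- **Section 10.5:** say that the 10% covers loss to follow-up only, and give the power at one or more lower ATP numbers, for example 87.5% at 91 per arm and about 81% at 79 per arm (score method, 0.97 in both arms).
- **Section 10.5.3:** make no change on the basis of the immunogenicity retention rate.

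The cost is protocol wording only: no extra infants, visits or samples. The stated power becomes somewhat less favourable.
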